11.7.2. ECG

ECG Parameter	Units	Clinical Concern Range	
		Lower	Upper
Absolute			
Absolute QTc Interval	msec	> 450	
Absolute PR Interval	msec	< 110	> 220
Absolute QRS Interval	msec	< 75	> 110
Change from Baseline			
Increase from Baseline QTc	msec	> 60	

11.7.3. Vital Signs

Vital Sign Parameter (Absolute)	Units	Clinical Concern Range	
		Lower	Upper
Systolic Blood Pressure	mmHg	< 85	> 160
Diastolic Blood Pressure	mmHg	< 45	> 100
Heart Rate	bpm	< 40	> 110

11.8. Appendix 8: Laboratory A&R Dataset Details

Panel ^[1]	Parameter	Unit	Normal Range		Anticipated Direction of Change with Treatment
			Low	High	
Fasted Chemistry	Serum Albumin	G/L	32	50	Safety laboratory parameters not expected to change
	Alkaline Phosphatase	IU/L	20	125	
	ALT	IU/L	0	48	
	AST	IU/L	0	42	
	BUN (UREA)	MMOL/L	2.5	10.5	
	Calcium	MMOL/L	2.12	2.56	
	Chloride	MMOL/L	95	108	
	Creatinine	UMOL/L	67.2	129.1	
	Creatinine Clearance	N/A	N/A	N/A	
	Direct Bilirubin	UMOL/L	0	6	
	GGT	IU/L	0	75	
	Glucose, fasting	MMOL/L	3.9	5.5	
	Potassium	MMOL/L	3.5	5.3	
	Sodium	MMOL/L	135	146	
Lipid	Total Bilirubin	UMOL/L	0	22	Safety laboratory parameters not expected to change
	Total Protein	G/L	60	85	
	Uric Acid	UMOL/L	240	510	
	HDL	MMOL/L	0.9	99.99	
Urinalysis	LDL (Calculated)	MMOL/L	0	3.35	Not able to specify specifically.
	Total Cholesterol	MMOL/L	0	5.15	
	Triglycerides	MMOL/L	0	2.24	
	Blood	Dipstick	N/AP	N/AP	
	Bacteria	Microy	N/AP	N/AP	
	Hyaline Casts (N/A)	N/A	N/AP	N/AP	
	Nitrite	Dipstick	N/AP	N/AP	
	Protein	Dipstick	N/AP	N/AP	
Haematology	RBC	Microscopy	N/AP	N/AP	Safety laboratory parameters not expected to change
	Specific Gravity	N/A	N/AP	N/AP	
	WBC	GI/L	3.8	10.8	
	Basophils	GI/L	0	0.2	
	Eosinophils	GI/L	0.05	0.55	
	Hemoglobin	G/L	118	168	
	Hematocrit	1	0.41	0.5	
	Lymphocytes	GI/L	0.85	4.1	
	MCV	FL	82	103	
	MCH	PG	27	33	
	MCHC	G/L	320	360	
	Monocytes	GI/L	0.2	1.1	

NOTE :

- N/A = Not available on DM dataset during RAP completion.
- N/AP = No ranges are normally provided for parameters.

11.9. Appendix 9: Biomarker A&R Dataset Details

Parameters (BICATCD Code)	Sample	Unit	LLQ	ULQ
Dataset : Biomark (QUEST)				
Adiponectin (ADPN)	Serum	MG/L	2	61
Albumin (ALB)	Urine	MG/L	3	9999
Creatinine (CREAT)	Urine	MMOL/L	0.2	999999.9
C-peptide (MMT) (CPEP)	Serum	NMOL/L	0.1	9999.99
C-Reactive Protein, Highly Sensitive (CRPHS)	Serum	MG/L	0.3.	800
CXCL10 / IP-10 (IP10)	Serum	NG/L	54.5	56000
Fructosamine (FRUC)	Serum	UMOL/L	20	1000
Glucose (MMT) (GLUC)	Plasma	MMOL/L	1.1	277.5
Glucagon (MMT) (No data for IA)	Plasma	N/A	N/A	N/A
Glycohemoglobin A1c (HbA1c)	Whole Blood	MMOL/L	3	18.9
Highly Sensitive Interleukin-6 (IL-6)	Serum	NG/L	0.156	640
Insulin (MMT) (INS)	Serum	PMOL/L	12	99999
Intercellular Adhesion Molecule, Soluble (sICAM)	Serum	NG/L	312	3200000
Matrix Metalloproteinase-9 (MMP-9)	Serum	NG/L	975	40000000
Non-Esterified Fatty Acids (NEFA)	Serum	MMOL/L	0.03	9
Monocyte Chemotactic protein-1 (MCP1)	Urine	NG/L	3.12	800
Plasminogen Activator Inhibitor-1 (PAI-1)	Plasma	NG/L	153	20000000
Resistin (RESIST)	Serum	MCG/L	0.8	800
Dataset : IMGEN (GSK Clinical Immunology)				
Interleukin 18 – Complex (IL18C)	Serum	pg/mL	19.5	N/AP
Interleukin 18 – Free (IL8F)	Serum	pg/mL	4	N/AP

NOTE :

- Urine biomarkers will be reported as ratios to creatinine i.e. Albumin/creatinine (ACR) and MCP-1/creatinine.
- N/A - Not available on DM dataset during RAP completion.
- N/AP = No ranges are normally provided for parameters.

11.10. Appendix 10 – Abbreviations & Trade Marks

11.10.1. Abbreviations

Abbreviation	Description
AE	Adverse Event
GSK	GlaxoSmithKline
AE	Adverse Event
ALT	Alanine aminotransferase (SGPT)
AST	Aspartate aminotransferase (SGOT)
AUC	Area under concentration-time curve
AUC($0-\infty$)	Area under the concentration-time curve from time zero (pre-dose) extrapolated to infinite time
BMI	Body mass index
BPM	Beat Per Minute
BQL	Below the quantification limit
CL	Systemic clearance of parent drug
Cmax	Maximum observed concentration
CI	Confidence Interval
CPMS	Clinical Pharmacology Modelling & Simulation
CPSR	Clinical Pharmacology Study Report
CS	Clinical Statistics
CPSSO	Clinical Pharmacology Science and Study Operations
CV	Coefficient of variance
DM	Data Management
FPG	Fasting Plasma Glucose
GSK	GlaxoSmithKline
HOMA-%B	Homeostasis Model Assessment (β -cell function)
HOMA-%S	Homeostasis Model Assessment (Insulin sensitivity)
HR	Heart rate
ICH	International Conference on Harmonization of Technical Requirements for Registration of Pharmaceuticals for Human Use
IDS	Integrated Data Standards Library
IL	Interleukin
Kg	Kilogram
λ_z	Terminal phase rate constant
LLQ	Lower limit of quantification
MMRM	Mixed models repeated measures
MMT	Mixed Meal Test
msec	Milliseconds
NQ	Non-quantifiable concentration measured as below LLQ
OB	Obese
PK	Pharmacokinetic
QC	Quality control
QTc	QT duration corrected

Abbreviation	Description
QTcB	QT duration corrected for heart rate by Bazett's formula
QTcF	QT duration corrected for heart rate by Fridericia's formula
RAP	Reporting and Analysis Plan
RNA	Ribonucleic acid
SAS	Statistical Analysis Software
SI	System Independent
STAT	Signal transducer and activator of transcription
SD	Standard deviation
SOP	Standard Operating Procedure
T	Infusion duration
t OR tlast	Time of last observed quantifiable concentration
t½	Terminal phase half-life
τ	Dosing interval
tlag	Lag time before observation of drug concentrations in sampled matrix
tmax	Time of occurrence of Cmax
TNF-α	Tumour necrosis factor – alpha
ULQ	Upper limit of quantification
ULN	Upper limit of normal
UK	United Kingdom
VAS	Visual analogue score
Vss	Volume of distribution at steady state
WBA	Whole blood assay
WBC	White blood cells

11.10.2. Trademarks

Trademarks of the GlaxoSmithKline Group of Companies	Trademarks not owned by the GlaxoSmithKline Group of Companies
NONE	NONMEM SAS WinNonlin

11.13. Appendix 11: List of Data Displays

11.13.1. Data Display Numbering

The following numbering will be applied for RAP generated displays:

Section	Tables	Figures
Study Population	1.01 to 1.11	N/A
Efficacy	2.01 to 2.32	2.01 to 2.72
Safety	3.01 to 3.21	N/A
Pharmacokinetic	4.01 to 4.05	4.01 to 4.02
Section	Listings	
ICH Listings		1 to 23
Other Listings		24 to 41

The numbering of the TLF's below is a suggestion and can be altered by the programmers if needed. If the programmers need to change the numbering, please add new numbers to the end of the sequence.

11.13.2. Deliverable [Priority]

Delivery Priority ¹	Description
IA	"Interim" Analysis Part A (after completion of approximately 6 patients)
SAC 2	Part A Final Statistical Analysis Complete

11.13.3. Mock Example Numbering

Non IDSL specifications will be referred as detailed below and where appropriate an example mock-up table is provided in [Appendix 12](#):

Section	Figure	Table	Listing
Study Population	POP_Fn	POP_Tn	POP_Ln
Efficacy	EFF_Fn	EFF_Tn	EFF_Ln
Safety	SAFE_Fn	SAFE_Tn	SAFE_Ln
Pharmacokinetic	PK_Fn	PK_Tn	PK_Ln

NOTE:

- Non-Standard displays are indicated in the IDSL / TST ID / Example Shell' or Programming Notes' column as '[Non-Standard] + Reference.'

11.13.4. Study Population Tables

Study Population Tables					
No.	Population	IDSL / TST ID / Example Shell	Title	Programming Notes	Deliverable [Priority]
Subject Disposition					
1.01	All Subjects	ES1	Summary of Subject Disposition		SAC [2]
1.02	Screening Population	ES6	Summary of Reasons for Screening Failure		SAC [2]
1.03	All Subjects	ES5	Summary of Reasons for Withdrawals		SAC [2]
1.04	All Subjects	DV1a	Summary of Important Protocol Deviations		SAC [2]
1.05	All Subjects	SA2	Summary of Deviations Leading to Exclusion from Per Protocol Population		SAC [2]
Demographics					
1.06	All Subjects	DM1	Summary of Demographic Characteristics	Make twice, pooled and by site	IA, SAC [2]
1.07	All Subjects	DM5	Summary of Race and Racial Combinations	Make twice, pooled and by site	SAC [2]
1.08	Enrolled	DM11	Summary of Age Ranges		SAC [2]
1.12	Enrolled	NS1	Summary of Number of Subjected by Country and Site ID		SAC[2]
1.09	All Subjects	SA1	Summary of Study Populations		SAC [2]
Medical Condition & Con Meds					
1.10	All Subjects	MH1	Summary of [Current/Past] Medical Conditions	Make twice, pooled and by site	SAC [2]

Study Population Tables					
No.	Population	IDSL / TST ID / Example Shell	Title	Programming Notes	Deliverable [Priority]
1.11	All Subjects	CM1	Summary of Most Frequently used Concomitant Medications by Generic Term	Footnote: Most Frequently means the overall concomitant medication used is $\geq 10\%$	SAC [2]

11.13.5. Efficacy Tables

Efficacy Tables					
No.	Population	IDSL / TST ID / Example Shell	Title	Programming Notes	Deliverable [Priority]
DLco					
2.01	Analysis	Non-Standard EFF_T1	Summary Statistics of DLco	DLco has measures on Baseline, Day 4, 5, and 7 for each treatment period and follow-up. Create this table twice, one table with only Mayo patients and another table with only Hennepin patients	IA, SAC [2]
2.02	Analysis	Non-Standard EFF_T2	Summary Statistics of DLco Change from Baseline	Create this table twice, one table with only Mayo patients and another table with only Hennepin patients	IA, SAC [2]
2.03	Analysis	Non-Standard EFF_T12	Summary Statistics of DLco Change from Intervention	Create this table twice, one table with only Mayo patients and another table with only Hennepin patients. This should be the Mean and SD of the Post-Pre difference.	IA, SAC [2]
2.04	Analysis	Non-Standard EFF_T6	Summary of Statistical Analysis Results of DLco	Models should be run with only Mayo patients. Hennepin patients are excluded because of methodological differences.	IA, SAC [2]
Alveolar-capillary Conductance (D_M)					
2.05	Analysis	Non-Standard EFF_T3	Summary Statistics of Gas Transfer Tests	DLno, Dm, Vc, and Dm/Vc have measures on Baseline, Day 4, 5, and 7 for each treatment period and follow-up	SAC [2]
2.06	Analysis	Non-Standard EFF_T2	Summary Statistics of Gas Transfer Tests Change from Baseline	DLno, Dm, Vc, and Dm/Vc have measures on Baseline, Day 4, 5, and 7 for each treatment period and follow-up. Baseline is day -1 for exercise and chronic values, but should be calculated as post minus pre for Saline.	SAC [2]

Efficacy Tables					
No.	Population	IDSL / TST ID / Example Shell	Title	Programming Notes	Deliverable [Priority]
2.07	Analysis	Non-Standard EFF_T12	Summary Statistics of Gas Transfer Tests Change from Intervention	DLno, Dm, Vc, and Dm/Vc have measures on Baseline and Day 5 and 7 for each treatment period. This should be the Mean and SD of the Post-Pre difference.	IA, SAC [2]
Ventilatory Efficiency					
2.08	Analysis	Non-Standard EFF_T7	Summary Statistics of VE/VCO ₂ Ratio	VE/VCO ₂ ratio has measures on Baseline and Day 7 before and after 3-minutes step test. Create this table twice, one table with all patients and another table with Hennepin patients excluded from the statistics.	SAC [2]
2.09	Analysis	Non-Standard EFF_T8	Summary Statistics of VE/VCO ₂ Ratio Change from Baseline	VE/VCO ₂ ratio has measures on Baseline and Day 7 before and after 3-minutes step test. Create this table twice, one table with all patients and another table with Hennepin patients excluded from the statistics.	SAC [2]
Pulmonary Function					
2.10	Analysis	Non-Standard EFF_T4	Summary Statistics of Pulmonary Function Tests	Pulmonary function (FVC, FEV ₁ , FEF ₂₅₋₇₅ , FEF ₅₀ , FEF ₇₅) has measures on Baseline, Day 4 and Day 7 for each treatment period. Pool all patients.	SAC [2]
2.11	Analysis	Non-Standard EFF_T5	Summary Statistics of Pulmonary Function Tests Change from Baseline	Pulmonary function (FVC, FEV ₁ , FEF ₂₅₋₇₅ , FEF ₅₀ , FEF ₇₅) has measures on Baseline, Day 4, and Day 7 for each treatment period. Pool all patients.	SAC [2]
2.12	Analysis	Non-Standard EFF_T4	Summary Statistics of Pulmonary Function Tests by Site	Pulmonary function (FVC, FEV ₁ , FEF ₂₅₋₇₅ , FEF ₅₀ , FEF ₇₅) has measures on Baseline, Day 4 and Day 7 for each treatment period. Create this table twice, one table with Mayo patients and another table with Hennepin patients.	SAC [2]

Efficacy Tables					
No.	Population	IDSL / TST ID / Example Shell	Title	Programming Notes	Deliverable [Priority]
2.13	Analysis	Non-Standard EFF_T5	Summary Statistics of Pulmonary Function Tests Change from Baseline by Site	Pulmonary function (FVC, FEV ₁ , FEF ₂₅₋₇₅ , FEF ₅₀ , FEF ₇₅) has measures on Baseline, Day 4, and Day 7 for each treatment period. Create this table twice, one table with Mayo patients and another table with Hennepin patients.	SAC [2]
Dyspnea					
2.14	Analysis	Non-Standard EFF_T9	Summary Statistics Dyspnea Score	Dyspnea Score has measures at Baseline pre and post exercise, Day 5 pre-saline sitting and supine, Day 7 pre and post exercise for each treatment period and at follow-up pre and post exercise	SAC [2]
2.15	Analysis	Non-Standard EFF_T5	Summary Statistics Change from Baseline Dyspnea Score	Dyspnea Score change from baseline has measures at Baseline post exercise, Day 5 pre-saline sitting and supine, Day 7 pre and post exercise for each treatment period and at follow-up pre and post exercise	SAC [2]
SF-36 score					
2.16	Analysis	SF2	Summary Statistics SF-36 Score	SF-36 Score has measures at Baseline and Day 7 for each treatment period and follow-up. Add additional rows for questions 3a to 3j to be looked at along with the domain scores	SAC [2]
2.17	Analysis	SF4	Summary Statistics of Change from Baseline SF-36 Score	SF-36 Score change from Baseline has a measure at Day 7 for each treatment period and follow-up. Add additional rows for questions 3a to 3j to be looked at along with the domain scores	SAC [2]

Efficacy Tables					
No.	Population	IDSL / TST ID / Example Shell	Title	Programming Notes	Deliverable [Priority]
Troponin					
2.18	All Subject	LB1	Summary Statistics of Troponin		SAC [2]
2.19	All Subject	LB3	Summary Statistics of Troponin Change from Baseline		SAC [2]
Respiratory Rate					
2.20	All Subject	EFF_T11	Summary Statistics of Respiratory Rate		SAC [2]

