11.4.2. Baseline Definition & Derivations

11.4.2.1. Baseline Definitions

For all endpoints baseline value will be taken on Day -1 for each treatment period, unless otherwise specified.

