11.4.2.2. Derivations and Handling of Missing Baseline Data

Definition	Reporting Details
Change from Baseline	= Post-Dose Visit Value – The corresponding Baseline
[% Change from Baseline]	= [(Post-Dose Visit Value – Baseline) / Baseline] x 100]

NOTE :

- Unless otherwise specified, the baseline definitions specified in [11.4.2.1Baseline Definitions](#) will be used for derivations for endpoints / parameters and indicated on summaries and listings.
- Unless otherwise stated, if baseline data is missing no derivation will be performed and will be set to missing.
- The baseline definition will be footnoted on all change from baseline displays.

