2.38	Analysis	Non-Standard EFF_F5	Plot of Change from Baseline for Chronic V_c by Individual and Treatment	Only pre-challenge V_c values	SAC [2]
2.39	Analysis	Non-Standard EFF_F6	Mean (95% CI) Plot of V_c Change from Baseline	V_c has means at Baseline, Day 4, Day 5, and Day 7 for each treatment and includes pre/post exercise and saline challenge. Baseline is minus day -1 for exercise and no challenge, but should be calculated as post minus pre for Saline.	SAC [2]
2.40	Analysis	Non-Standard EFF_F7	Mean (95% CI) Plot of Exercise V_c	V_c has measures at Baseline and Day 7 for each treatment and a follow-up. Graph should include pre/post exercise values.	SAC [2]

Efficacy Figures					
No.	Population	IDSL / TST ID / Example Shell	Title	Programming Notes	Deliverable [Priority]
2.41	Analysis	Non-Standard EFF_F8	Mean (95% CI) Plot of Change from Exercise for Vc	Vc has means at Baseline and Day 7 for each treatment and a follow-up. The bars represent the mean change from just prior to exercise to post exercise. mean(Post-Pre)	SAC [2]
2.42	Analysis	Non-Standard EFF_F23	Forest Plot of DL End Points Change	Forest plot of DLco, DLno, Vc, and Dm change from baseline to day 7, change from pre and post saline for DLco and change from pre/post exercise on day 7 for DLco. Include the mean absolute change next to the box plot as seen in the mock-up	SAC[2]
2.43	Analysis	Non-Standard EFF_F9	Mean (95% CI) Plot of Percent Change from Exercise for Vc	Vc has means at Baseline and Day 7 for each treatment and a follow-up. The bars represent the mean percent change from just prior to exercise to post exercise.	SAC [2]
2.44	Analysis	Non-Standard EFF_F10	Mean (95% CI) Plot of Percent Change from Saline for Vc	Vc has means at Day 5 for each treatment and a follow-up. The bars represent the mean percent change from just prior to exercise to post saline infusion.	SAC [2]
Ventilatory Efficiency					
2.45-	Analysis	Non-Standard EFF_F11	Plot of VE/VCO ₂	Has 5 measures at Baseline, Day 7, and Follow-Up	SAC[2]
2.46	Analysis	Non-Standard EFF_F12	Mean (95% CI) Plot of VE/VCO ₂	Has means for each of the 5 measures at baseline, Day 7 and Follow-Up	SAC[2]
2.47	Analysis	Non-Standard EFF_F13	Plot of VE/VCO ₂ Change from Day -1	Is the difference between day -1 and day 7 for each time point in the exercise test (e.g. at rest day 7 – at rest day -1, post 1 min day 7 - post 1 min day -1)	SAC[2]

Efficacy Figures					

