2.62	Analysis	Non-Standard EFF_F19	Mean (95% CI) Plot of FEF ₅₀ Change from Baseline	FEF ₅₀ has means at Day 4 and Day 7.	SAC[2]
2.63	Analysis	Non-Standard EFF_F17	Spaghetti Plot of FEF ₇₅	FEF ₇₅ has means at Baseline, Day 4 and Day 7 for each treatment and a follow-up measure	SAC[2]
2.64	Analysis	Non-Standard EFF_F18	Mean (95% CI) Plot of FEF ₇₅	FEF ₇₅ has means at Baseline, Day 4 and Day 7 for each treatment and a follow-up measure	SAC[2]

Efficacy Figures					
No.	Population	IDSL / TST ID / Example Shell	Title	Programming Notes	Deliverable [Priority]
2.65	Analysis	Non-Standard EFF_F19	Mean (95% CI) Plot of FEF ₇₅ Change from Baseline	FEF ₇₅ has means at Day 4 and Day 7.	SAC[2]
2.66	Analysis	Non-Standard EFF_F23	Forest Plot of Pulmonary Function Test	Forest plot of FVC, FEV ₁ , FEF ₂₅₋₇₅ , FEF ₅₀ , FEF ₇₅ . Include the mean absolute change next to the box plot as seen in the mock-up	SAC[2]
Dyspnea					
2.67	Analysis	Non-Standard EFF_F17	Spaghetti Plot of Dyspnea	Dyspnea has measures at Baseline pre and post exercise, Day 5 pre-saline sitting and supine, and Day 7 pre and post exercise	SAC[2]
2.68	Analysis	Non-Standard EFF_F18	Mean (95% CI) Plot of Dyspnea	Dyspnea has means at Baseline pre and post exercise, Day 5 pre-saline sitting and supine, and Day 7 pre and post exercise.	SAC[2]
2.69	Analysis	Non-Standard EFF_F19	Mean (95% CI) Plot of Dyspnea Change from Baseline	Dyspnea has means at Baseline post exercise, Day 5 pre-saline sitting and supine, and Day 7 pre and post exercise	SAC[2]
SF-36 Score					
2.70	Analysis	Non-Standard EFF_F19	Mean (95% CI) Plot of SF-36 Acute Score Change from Baseline	SF-36 Acute Score has means at Day -1 and Day 7	SAC[2]
Respiratory Rate					
2.71	All Subject	Non-Standard EFF_F20	Individual Plot of 24-Hour Respiratory Monitoring	There will be a graph for each patient individually	SAC[2]
2.72	All Subject	Non-Standard EFF_F21	Mean (95% CI) Plot of 24 Hour Respiratory Rate Monitoring		SAC[2]

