 Population : Analysis

Page 1 of X

Table 1.09
 Summary Statistics of Dyspnea

Visit	Treatment	N	n	Mean	SD	Median	Range	Percent of Patients with at Least 1-Point Improvement ¹	Frequency of Item Scores				
									1	2	3	4	5
Baseline Pre-Exercise	A	X	X	XX.X	XX.XX	XX.X	X - X		X	X	X	X	X
Baseline Post-Exercise	A	X	X	XX.X	XX.XX	XX.X	X - X	XX.XX	X	X	X	X	X
Day 5 Sitting	A	X	X	XX.X	XX.XX	XX.X	X - X	XX.XX	X	X	X	X	X
Day 5 Supine	A	X	X	XX.X	XX.XX	XX.X	X - X	XX.XX	X	X	X	X	X
Day 7 Pre-Exercise	A	X	X	XX.X	XX.XX	XX.X	X - X	XX.XX	X	X	X	X	X
Day 7 Post-Exercise	A	X	X	XX.X	XX.XX	XX.X	X - X	XX.XX	X	X	X	X	X
Baseline Pre-Exercise	B	X	X	XX.X	XX.XX	XX.X	X - X		X	X	X	X	X
Baseline Post-Exercise	B	X	X	XX.X	XX.XX	XX.X	X - X	XX.XX	X	X	X	X	X
Day 5 Sitting	B	X	X	XX.X	XX.XX	XX.X	X - X	XX.XX	X	X	X	X	X
Day 5 Supine	B	X	X	XX.X	XX.XX	XX.X	X - X	XX.XX	X	X	X	X	X
Day 7 Pre-Exercise	B	X	X	XX.X	XX.XX	XX.X	X - X	XX.XX	X	X	X	X	X
Day 7 Post-Exercise	B	X	X	XX.X	XX.XX	XX.X	X - X	XX.XX	X	X	X	X	X
Follow-up	NA	X	X	XX.X	XX.XX	XX.X	X - X		X	X	X	X	X

Example : EFF_T11
 Protocol : 201881
 Population : Analysis

Page 1 of X

Table 1.11
 Summary Statistics of Respiratory Rate

Day -1				Day 4				Day 7			
Treatment		Placebo		Treatment		Placebo		Treatment		Placebo	
Mean	SD	Number of Hours Included	Mean	SD	Number of Hours Included	Mean	SD	Number of Hours Included	Mean	SD	Number of Hours Included

Lying
 Standing
 Leaning

Example : EFF_T12
Protocol : 201881
Population : Analysis

Page 1 of X

Table 1.12
Summary Statistics of DLco Change from Intervention

Visit	Treatment	N	n	Mean	SD
Baseline change from exercise	A	X	X	XX.X	XX.XX
Day 5 change from saline infusion	A	X	X	XX.X	XX.XX
Day 7 change from exercise	A	X	X	XX.X	XX.XX
Baseline change from exercise	B	X	X	XX.X	XX.XX
Day 5 change from saline infusion	B	X	X	XX.X	XX.XX
Day 7 change from exercise	B	X	X	XX.X	XX.XX

Example : EFF_L1
Protocol : 201881
Population : All Subjects

Page 1 of X

Listing 1
Listing of Gas Diffusion

Sequence	Treatment	Subject	Visit	DLco	DLno	D _M	VE/VCO ₂
AB		1	Screening				
			Period 1 Baseline				
	A		Period 1 Day -1 Post Exercise				
	A		Period 1 Day 4				
	A		Period 1 Day 5				
	B		Period 1 Day 5 Post-Saline				
			Period 2 Baseline				
	B		Period 2 Day -1 Post Exercise				
	B		Period 2 Day 4				
	B		Period 2 Day 5				
	B		Period 2 Day 5 Post-Saline				
			Follow-Up				

Example : EFF_L2
Protocol :
Population : Safety

Page 1 of X

Listing 2
Listing of Gas Diffusion Change from Baseline

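### Dyspnea change and the 1-point improvement percentage at Day 7 post-exercise and Day 5 supine are referred to the Day -1 pre-exercise score, so exertion or posture enters the within-treatment change and subjects are misclassified as improved or not

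*SAP*

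**What the plan says.** Dyspnea is a secondary endpoint on a 5-point scale. SAP section 11.13.5 sets out two tables. For the raw scores, Table 2.14 states: "Dyspnea Score has measures at Baseline pre and post exercise, Day 5 pre-saline sitting and supine, Day 7 pre and post exercise". For change, Table 2.15 states: "Dyspnea Score change from baseline has measures at Baseline post exercise, Day 5 pre-saline sitting and supine, Day 7 pre and post exercise". Figure 2.69, the change plot, has the same pattern: "Dyspnea has means at Baseline post exercise, Day 5 pre-saline sitting and supine, and Day 7 pre and post exercise".

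The mock shell for Table 2.14 is EFF_T9 in SAP Appendix 12. It has a column headed "Percent of Patients with at Least 1-Point Improvement". The cell is blank for Day -1 pre-exercise and for follow-up. It is filled for Day -1 post-exercise, Day 5 sitting, Day 5 supine, and Day 7 pre- and post-exercise, under both treatments. The heading carries a footnote marker whose text is not in the copy reviewed.

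The general rules do not settle the reference. SAP 11.4.2.1 says: "For all endpoints baseline value will be taken on Day -1 for each treatment period, unless otherwise specified". SAP 11.4.2.2 defines change as "Post-Dose Visit Value – The corresponding Baseline". Neither mentions exercise state or posture.

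Elsewhere the SAP is more specific. For VE/VCO2, Figure 2.47 matches by exercise time point: "Is the difference between day -1 and day 7 for each time point in the exercise test", for example "post 1 min day 7 - post 1 min day -1". For DLco, Table 2.03 isolates the post-minus-pre challenge effect in a table of its own. Dyspnea has neither.

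**The concern.** A post-exercise score set against a resting score measures the step test and the treatment together. A supine score set against a baseline not described as supine measures posture and treatment together. The matched post-exercise score on Day -1 is collected, but it appears only as one more change row.

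The plan gives readers no between-treatment dyspnea estimate to fall back on. Protocol 9.4.2 foresaw a model like that for DLco, as data permit, but SAP Table 4 marks no statistical analysis for dyspnea. What will be reported is change and improvement percentage by treatment, and those are the quantities that the mismatch distorts. An improvement percentage before the first dose of a period has no treatment meaning at all.

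**Working it through.** The documents give no power, rate or expected change for dyspnea, so there is no planned figure to reproduce.

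**Step 1: which score is the reference?** Compare Tables 2.14 and 2.15, leaving aside follow-up, which belongs to neither treatment. Table 2.15 keeps every time point except Day -1 pre-exercise. If post-exercise rows used a post-exercise reference, the Day -1 post-exercise row would be a score minus itself: zero for everyone, with 0% improved. Listing it as a change row makes sense only against the pre-exercise score. No rule is given that would switch reference between rows.

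**Step 2: effect on one subject.** Assume higher is worse; the scale text is redacted, and if it runs the other way the signs mirror. Let S = (Day -1 post-exercise) - (Day -1 pre-exercise), and let M = (Day -1 post-exercise) - (Day 7 post-exercise), the matched improvement. The improvement as laid out is

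(Day -1 pre-exercise) - (Day 7 post-exercise) = M - S.

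Counting as improved needs M - S ≥ 1, that is M ≥ 1 + S. With S = 1 a matched fall of 2 points is needed; with S = 2, a fall of 3. If S is negative, a subject can count as improved without a matched 1-point fall.

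Example: rest 2, Day -1 post-exercise 4, Day 7 post-exercise 3. Matched change is 3 - 4 = -1 (improved). As laid out it is 3 - 2 = +1 (worse, not improved).

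**Step 3: effect on the means.** Within a treatment, the mean post-exercise change is raised by mean S. A shift of 1.0 with a benefit of 0.5 gives 1.0 - 0.5 = +0.5, which reads as worsening. Between treatments,

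(difference as laid out) = (matched difference) + (mean S in active periods - mean S in placebo periods).

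S is measured before dosing in each period, so with randomised sequences and no carryover the last bracket has expectation zero. It adds noise, not bias. The matched mean can also be recovered as the Day 7 post-exercise row minus the Day -1 post-exercise row in the same subjects; in the example, +1 - (+2) = -1. Its SD and the matched improvement percentage cannot be recovered from those rows.

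**Step 4: illustration of the percentage.** All inputs are assumed: resting mean 1.5 to 2.5 (SD 0.7), visit noise SD 0.4, exertion shift 0 to 1.5, benefit 0.5 or 1.0, scores rounded and held within 1 to 5, with 400,000 simulated subjects per setting. For resting mean 2.0 and benefit 1.0, Day 7 post-exercise (percentage differences are from unrounded rates):

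| Shift | As laid out: active / placebo / difference (%) | Matched: active / placebo / difference (%) | Mean difference: as laid out / matched |
|---|---|---|---|
| 0 | 62.7 / 20.0 / 42.7 | 62.7 / 19.9 / 42.7 | -0.732 / -0.734 |
| 0.5 | 43.1 / 5.5 / 37.5 | 73.1 / 21.4 / 51.7 | -0.892 / -0.893 |
| 1.0 | 19.9 / 0.9 / 19.0 | 77.2 / 21.5 / 55.7 | -0.968 / -0.970 |
| 1.5 | 5.6 / 0.1 / 5.5 | 78.0 / 21.3 / 56.7 | -0.989 / -0.987 |

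Across all settings with a shift of 0.5 to 1.5, between 42% and 98% of active-treatment subjects with a matched 1-point improvement were not counted. With no shift, noise alone gave 16% to 39%. The mean difference agreed within 0.002 in every setting.

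**Step 5: granularity.** SAP 4.1 records 10 subjects and a decision to enrol one more. With about 11 subjects, each reclassified subject moves a percentage by 1/11, about 9 points.

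**The case against.** The strongest reply is that little is lost. The endpoint is change in score, and the treatment difference in mean change is unbiased. EFF_T9 shows the mean, SD and full score frequencies for both post-exercise time points. Listing 37 gives individual dyspnea scores with change, so with about 11 subjects a matched count could be made by hand if the listing carries the same time points. The display is descriptive, and SAP section 2 records that the heart failure programme was not being continued.

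It can also be said that the reference is inferred. The follow-up cell in EFF_T9 is blank too, so a blank does not by itself identify the baseline, and the missing footnote might define it.

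The point about means stands in full. The point about inference stands for the improvement column, which rests on layout; for Table 2.15 and Figure 2.69 the inference is strong, for the reason in Step 1. That a reader could rebuild a matched count does not make the printed percentage right.

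A reader might go further and infer that the baseline hides a real drug benefit, that the percentage is driven to zero in both arms, or that many improved subjects are lost. The documents support none of these. Exertion and posture drop out of the mean contrast. Even in the illustration the percentage under active treatment can remain well above zero. How many are lost depends on an exertion shift that the documents do not give. Nor is the floor at a resting score of 1 caused by the mismatch: matching does not remove it from the resting rows.

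**Conclusion.** The point holds for Day 7 post-exercise and Day 5 supine. In those rows, the within-treatment change carries the exertion or posture effect, and the improvement percentage misclassifies subjects, which can shrink its active-placebo contrast. The pre-dose improvement cell at Day -1 post-exercise should not exist. Day 7 pre-exercise and Day 5 sitting are not affected.

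The size is unknown. The rule M ≥ 1 + S is exact under the inferred reference, but S is not documented, and the simulated rates rest on assumed inputs and an assumed scale direction. The supine part rests on neither document describing a supine Day -1 score; protocol Appendix 9 describes the supine assessment on Day 5. This is a descriptive secondary display, and the primary DLco result is unaffected.

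**What to change.** In Table 2.15, Figure 2.69 and shell EFF_T9:

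- Take Day 7 post-exercise change and 1-point improvement from the same period's Day -1 post-exercise score.
- Keep Day 7 pre-exercise and Day 5 sitting against Day -1 pre-exercise.
- Leave the improvement cell blank for Day -1 post-exercise and Day 5 supine.
- Report Day 5 supine as supine minus sitting on the same day.
- Show post-minus-pre exercise on Day -1 and Day 7 separately, as Table 2.03 does for DLco.

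State the reference for each row in a footnote, and give Table 2.15 a shell that fits: it now points to EFF_T5, which has only Day 4 and Day 7 rows. The cost is SAP wording and minor programming; no new data are needed.
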